Academy of Neurology to be the first-line intervention for tics.⁶ Immediately prior to each CBIT session, participants will undergo TMS targeting the SMA. The specific type of TMS procedure will be randomly assigned between subjects and be either: 1 Hz repetitive TMS (rTMS), continuous theta burst stimulation (cTBS), or sham stimulation.

4.2. Drug/Device Handling:

TMS device. Stimulation will be delivered using a Magstim Super Rapid2 stimulator (Magstim Company Ltd, UK). The device will be used to deliver electromagnetic stimulation through a small coil positioned over a targeted area on the scalp. The manufacturer's indication for use is to stimulate peripheral nerves and the human cortex for diagnostic and research purposes.

We will use a Magstim air-cooled 70mm figure-eight coil for motor threshold determination and active TMS conditions. Sham stimulation will use the Magstim sham air-cooled coil, which produces auditory signals identical to an active coil but contains a mu-metal shield that diverts the majority of the magnetic flux such that a minimal (<3%) magnetic field is delivered to the cortex.

The device is installed and set-up at the University of Minnesota Non-Invasive Neuromodulation Laboratory (NINL). The device will only be able to be administered by trained personnel. The device is located in a locked, access controlled room.

[figure not shown]
Operation of the TMS device (MAGSTIM Super Rapid 2) will follow the procedures outlined in the attached "Operating Manual."

- 4.3. Biosafety: N/A
- 4.4. Stem Cells: N/A
- 4.5. Fetal Tissue: N/A

5. Procedures Involved

5.1. **Study Design**: The study is a double-blinded randomized control trial that will examine whether combining Comprehensive Behavioral Intervention for Tics (CBIT) with inhibition of the

PROTOCOL TITLE: Transcranial Magnetic Stimulation to Augment Behavior Therapy for Tics VERSION DATE: 2/24/2022

supplementary motor area (SMA) using transcranial magnetic stimulation (TMS) normalizes activity in the SMA-connected circuits, improves tic suppression ability, and enhances CBIT outcomes in young people with tic disorder. We will compare two rTMS procedures, 1 Hz rTMS and continuous theta burst stimulation (cTBS), against sham stimulation. Youth with chronic tics (n = 60) will complete 10 daily sessions of CBIT plus randomly assigned TMS procedure, with fMRI, behavioral, and clinical assessments before and after treatment and at 1 and 3 month follow-ups (figure 1).

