- Tic Suppression Task (TST) procedures: The TST will be our primary measure of behavioral target engagement. In this paradigm, a participant is seated alone in a room in front of a computer capturing a video recording of tic occurrences for later coding by independent raters. TST will consist of two 3-min conditions: 1) free-to-tic (FT): youth is instructed to stay seated and tic freely, a measure of naturally occurring tic frequency (tics per minute) ; 2) suppression: youth is instructed to suppress tics. Videos will be coded to establish tic frequencies using a computerized behavioral coding program.
- Neuroimaging procedures. MRI and fMRI data acquisition: A Siemens Prisma 3T scanner located at the Center for Magnetic Resonance Research (CMRR) will be used for image acquisition. To minimize motion artifact, we will immobilize the participant's head with foam wedges that fit snugly between the head and 32channel receive only head coil. As needed, we will re-run scans or bring back participants for a repeat scan session. We will acquire the following data: 3D T1 ME-MPRAGE, 3D T2 SPACE, resting fMRI, spin Echo fMRI reverse phase encode scan pair, finger tapping task. The Finger Tapping Task will be used for functional localization of SMA. This task is used to isolate neural activity in

PROTOCOL TITLE: Transcranial Magnetic Stimulation to Augment Behavior Therapy for Tics VERSION DATE: 2/24/2022

motor planning and execution areas, including SMA, and is a highly reliable, well-established fMRI task used for motor mapping⁵³ and for TMS targeting of motor cortex and SMA by our group and others.³³ A whole-brain activation map showing the contrast of rest vs. active tapping will be created for each person to determine the precise placement of the TMS coil.

- **Randomization:** Randomization will occur after pre-treatment assessments. Randomization will be stratified on baseline TST performance (tic suppressibility below or above 50%) and medication status (on vs. off).
- Intervention Protocol: CBIT+TMS. TMS will be delivered immediately prior to the start of CBIT sessions (see figure 2).
- **CBIT Protocol** will follow the published CBIT manual⁵⁴ tested in the large trials that established CBIT efficacy in children and adults.^{8,9} Participants will receive 10 sessions of CBIT, 1 session per

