- **Premature Termination.** At any time, participants may deteriorate or develop clinical exigencies that lead study staff to recommend additional out-of-protocol treatments above and beyond that provided by ASAP guidelines (e.g., change in medications during the study). Such participants will be considered "premature terminators" (PMT) and classified as a protocol violation. In order to enhance the ITT analyses, "prematurely terminated" participants will continue to be treated within their assigned treatment arms insofar as possible, and assessments will continue according to protocol.
- Analysis population will be an intent-to-treat population including all enrolled participants who completed at least 1 CBIT session.
- Treatment of Missing Data: All participants will remain

PROTOCOL TITLE: Transcranial Magnetic Stimulation to Augment Behavior Therapy for Tics VERSION DATE: 2/24/2022

in the study unless consent is withdrawn or there are concerns about patient safety. While there is little that can be done to address missing data when participants drop out during the training process itself, we can compare baseline characteristics of those who drop out at this time versus those who do not and adjust models based on significant predictors of dropout. For those who drop out during the follow-up period or miss some assessments during followup, we will use multiple imputation by chained equations (MICE) to allow for missing data without loss of those cases from the model under the assumption of Missing at Random (MAR). Sensitivity Analysis: If dropout status appears to be Missing Not At Random (MNAR), i.e., dropout is associated with an unobserved outcome, we will run sensitivity analyses using MICE to compare imputed and non-imputed models results to assess robustness of statistical inference.

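### The planned check for data missing not at random compares two analyses that do not model it, so it cannot show robustness; the post-treatment outcomes also lack a stated imputation, and the analysis set is a modified ITT

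*Combined protocol and SAP*

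**What the plan says.** All of the missing-data rules are in protocol section 15.1.

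- **Analysis set.** "Analysis population will be an intent-to-treat population including all enrolled participants who completed at least 1 CBIT session". Section 5.2 says "Randomization will occur after pre-treatment assessments", and section 4.1 says "Immediately prior to each CBIT session, participants will undergo TMS targeting the SMA".
- **Dropout during treatment.** The plan says "there is little that can be done to address missing data when participants drop out during the training process itself". It then offers a comparison of baseline characteristics and adjustment for significant predictors of dropout. Premature terminators are kept: "participants will continue to be treated within their assigned treatment arms insofar as possible, and assessments will continue according to protocol".
- **Dropout in follow-up.** "For those who drop out during the follow-up period or miss some assessments during followup, we will use multiple imputation by chained equations (MICE" under a missing-at-random (MAR) assumption.
- **Sensitivity analysis.** The trigger is "If dropout status appears to be Missing Not At Random (MNAR", explained as dropout associated with an outcome that was not observed. In that case "we will run sensitivity analyses using MICE to compare imputed and non-imputed models results to assess robustness of statistical inference".

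Aims 1 and 2 are both analysed as change from pre- to post-treatment (section 15.1). Section 5.2 lists the post-treatment assessment separately from the 1- and 3-month follow-ups. Section 11.4 provides for two MRI scans. The last assessment offered to those who withdraw (section 12.2) leaves out the MRI.

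**The concern.** The sensitivity analysis is meant to protect against dropout that depends on the unseen outcome, but it has two faults. Its trigger asks for something the data cannot reveal: an association between dropout and values nobody has. Its content sets a MAR imputation beside an analysis without imputation, and neither contains an MNAR assumption. A report that the two agree, and that the result is therefore robust, would be unsupported.

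The scope of the imputation adds a gap. The main outcomes are measured at the post-treatment visit, while imputation is stated for follow-up. Someone who leaves during treatment is outside it. Someone who completes the ten sessions and misses only the post-treatment visit fits neither rule clearly.

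Last, a set that requires one completed CBIT session after randomisation and after the first TMS is not intent-to-treat in the usual sense.

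**Working it through.** **1. The plan's own figure.** Section 15.2 claims 80% power at eta-squared 0.18 after attrition, with no rate given. With f² = 0.18/0.82, noncentrality N·f² and alpha 0.05 (assumed), three-group ANOVA power is 89.6% at N = 60, just under 80% at N = 47 and 80.9% at N = 48. So 80% fits 48 of 60 analysed, or 20% lost. Other readings of the comparison give other rates. For two groups, N = 38 gives 80.2%: that is 19 of 20 per arm for one active arm against sham (5% lost), or 38 of 60 for pooled active against sham (37% lost). Dropout of 5 to 20% is used below, with 37% as an extreme.

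**2. Can agreement show robustness?** Assumptions: no true effect, outcome SD 1, pre-post correlation 0.5, and logistic dropout on the unseen post-treatment value (slope 0.5 weak, 1.5 strong) in one arm, random in the other. Imputation uses arm and baseline, because the plan names no variables. Large-sample bias in SD units (1,000,000 per arm):

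| Dropout | Change score | Baseline-adjusted, not imputed | MAR imputation |
|---|---|---|---|
| 5%, strong | 0.03 | 0.05 | 0.05 |
| 20%, weak | 0.05 | 0.07 | 0.07 |
| 20%, strong | 0.11 | 0.17 to 0.18 | 0.18 |

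With the same mechanism in both arms, every entry is within 0.01 of zero. Across 5, 10 and 20% dropout, weak or strong, in one arm or both, at correlations 0.3, 0.5 and 0.7, the baseline-adjusted and imputed estimates differ by at most 0.002 SD (0.006 SD with one common slope). They agree equally well when the bias is 0 and when it is 0.18. The 20% strong case gives 0.13 to 0.21 SD at correlations 0.7 to 0.3. At 37% strong the imputed bias is 0.23 to 0.37 SD.

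**3. Can disagreement identify MNAR?** Suppose dropout depends only on baseline, which is plain MAR. With pre-post correlation r and no effect, completers whose baseline mean is shifted by m have mean change (r − 1)m, or −0.5m at r = 0.5, while MAR imputation from baseline is unbiased. The two then differ although nothing is MNAR. Under MNAR they also differ, by 0.18 − 0.11 = 0.07 SD in the last row.

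**4. What a delta analysis adds.** Bias is the missing fraction times the departure of dropouts from their MAR prediction. In the last row the departure is 0.18/0.20 = 0.9 SD. Over all the 5 to 20% scenarios, dropouts were 0.25 to 1.19 SD worse than predicted. Each 1 SD of delta in one arm moves the arm difference by 0.05, 0.10 or 0.20 SD at 5, 10 or 20% missing. In 4,000 simulated trials of 20 per arm (last-row mechanism, truth 0), the mean difference was 0.17 at delta 0, 0.17 − 0.20 × 0.75 = 0.02 at delta 0.75, and 0.17 − 0.20 = −0.03 at delta 1.0.

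**5. Scale.** The standard error of a two-arm difference with 20 per arm (equal allocation assumed) is sqrt(2/20) = 0.32 SD.

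**6. The analysis set.** If the worst-tolerating 1 or 2 of 20 in one arm are excluded, mean tolerability shifts by 0.098 or 0.182 SD. At an assumed tolerability-outcome correlation of 0.1 to 0.5, the outcome mean shifts by 0.01 to 0.05 or 0.02 to 0.09 SD.

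**The case against.** **The plan does address treatment-phase loss.** It keeps premature terminators in assessment, offers withdrawn participants a last clinical visit, and adjusts for predictors of dropout. This stands in part. The last visit may recover a TST value but not the MRI. When only the outcome is missing, adjustment is valid under MAR given those covariates, so for Aim 1 imputation alone would hardly change the answer.

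**Extending MICE can look like a step backwards for Aim 2.** In the 20% strong case it raises the bias from 0.11 to 0.18 SD before any delta is applied. That is correct. The extension is worth making as the base for the delta analysis, not as a cure.

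**Follow-up may include the post-treatment visit.** The plan contrasts the training process with the follow-up period, so a missed post-treatment visit after ten sessions could be read as covered. Section 5.2 points the other way. This is an ambiguity; for dropout during treatment there is none.

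**The analysis-set point is mostly a label.** Largely so. Participants are blinded, so losses before the first TMS are unlikely to depend on arm. A reader might infer from the stated advantages of theta burst for children that early tolerability differs by arm. The same part of section 5.2 reports comparable safety for theta burst and conventional rTMS in children, so the documents do not support that inference.

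**Conclusion.** The main point holds on the text and needs no assumed rate: the MNAR check has a trigger that cannot be evaluated and compares two analyses without an MNAR model. Neither agreement nor disagreement answers the question it poses.

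Two stronger readings should be resisted. One is that the check can be given an error rate as planned. Read strictly, section 15.1 produces no imputed Aim 1 or Aim 2 result to compare, so any performance figure depends on extending MICE to those outcomes, on the variables chosen and on the dropout-predictor adjustment. The other is that the trial's result will be biased by 0.18 SD. That figure needs 20% strongly outcome-dependent dropout in one arm only. The change score named for Aim 2 gives 0.11 SD there, and a mechanism shared by the arms gives about zero. In all the 5 to 20% scenarios the bias is below the 0.32 SD standard error. The documents give no dropout rate or allocation ratio. The harm is an unsupported claim of robustness, not demonstrated bias.

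The imputation gap is secondary. The analysis-set label is minor, with an unknown and probably small number affected.

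**What to change.** (a) Replace the conditional comparison with a delta-adjusted (tipping-point) MICE analysis of the post-treatment Aim 1 and Aim 2 outcomes. Run it whatever the dropout looks like, and vary delta separately by arm, for example from 0 to 1.25 SD worse in steps of 0.25 SD, which spans the simulated departures. Report the delta, if any, at which the conclusion changes. The base imputation should cover both treatment-phase dropouts and missed post-treatment visits, name its variables, and be stated to assume MAR.

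(b) Define the primary set as all randomised participants, analysed as randomised. If the present set is kept, call it modified ITT.

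The cost is rewording of section 15.1 and modest extra analysis, with no new data collection. Intervals widen slightly: the simulated SD of the estimate was 0.317 with imputation and 0.315 without. The delta analysis shows how far the result depends on delta; it does not estimate delta.

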 - Sham: to enhance blinding, half of sham participants will be exposed to the 1 Hz sequence and half will be exposed to the cTBS sequence
 - Number of sessions: 10 day sessions, delivered daily on weekdays
 - Immediately after the stimulation ends, the participant will be transitioned to a private room for the CBIT session. The *TMS Adverse Effects Questionnaire³⁹* will be completed by the participant and TMS operator at the end of each study visit.
 - rTMS sessions will be video recorded to later be coded for tic occurrences.
- Blinding procedures will be implemented to control for expectancy effects related to TMS stimulation. Persons who will be blind to TMS status are: participants; parents (if applicable); study staff administering clinical assessments, coding TST videos, delivering CBIT therapy, and collecting the MRI data; and all study investigators except Drs. [name] and [name]. Unblinded personnel will be [name], the study statistician and person responsible for randomization scheme oversight; [name], TMS operator supervisor; and the TMS operator. Staff who administer clinical rating scales and code TST videos will not be present for a given participant's CBIT+TMS visits to also ensure blinding to overall therapy progress. Staff will be trained and supervised on assessment scales by [name], who will audit YGTSS administrations for inter-rater reliability. Staff will be trained in TST coding by [name], who will code a set of video clips to monitor inter-rater reliability. For each of these measures (YGTSS

PROTOCOL TITLE: Transcranial Magnetic Stimulation to Augment Behavior Therapy for Tics VERSION DATE: 2/24/2022

and TST), the supervisor will audit 100% of the first ¹/₃ of the initial visits, 50% of the second ¹/₃ of participants, and 20% of the third ¹/₃ of the participants for inter-rater reliability. Forms assessing blinding adequacy will be given to participants, parents, and blinded staff who conduct CBIT sessions and assessments visits at post-treatment.

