- 12.1. Withdrawal Circumstances: Anticipated circumstances under which participants will be withdrawn from the research without their consent include: 1) the participant does not/no longer meets inclusion/exclusion criteria; 2) study investigators decide that the participant has an emotional, physical, or behavioral reaction that poses a safety concern or interferes with data collection (e.g., poor compliance with instructions, too much anxiety to comfortably proceed with a task); 3) significantly deteriorating clinical course (e.g., emergence of acute suicidality); 4) significant adverse reaction to TMS, assessed using a TMS Symptom Rating Questionnaire daily; or 5) serious physical illness. Participants will be free to decide to withdraw at any time for any reason.
- 12.2. Withdrawal Procedures: Study withdrawals will be documented. When safe and feasible, participants who are withdrawn or who decide to terminate participation prematurely ("drop out") will be encouraged to return for a last assessment. This last assessment will consist of measures in the follow-up assessments (i.e., clinical measures only and not the MRI). We will make an attempt to provide participants with appropriate care referrals in the event of any withdrawals or drop-outs.
- 12.3. Termination Procedures: Individual participants will be considered to have completed study procedures after the 3-month follow-up assessment (or earlier as a result of drop-out or investigator-initiated withdrawal). The entire study will be complete after analysis of all identifiable data is complete. After termination of the project, only de-identified data will be used for analysis.

13. Risks to Participants

13.1. Foreseeable Risks:

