- TMS, uncomfortable sensations and pain: The most commonly reported side effects of TMS are headache (lasting up to a few hours) and pain or discomfort at the treatment site on the scalp. A large-scale study on the safety of rTMS in depression found that headaches or scalp discomfort were typically mild or moderate. Headaches and neck pain are believed to be due to muscle tension. rTMS will be terminated if it produces discomfort which is not tolerated by participants. If a bothersome headache persists for several hours (which we think is unlikely), participants may choose to use an OTC pain reliever such as acetaminophen or ibuprofen for pain.
- TMS, hearing: While temporary hearing loss is a theoretical risk of TMS, available data indicate TMS has no demonstrable effect on hearing. All participants will wear ear protection (34 NRR earplugs) during TMS. In order to inform and protect participants, we will take the following precautions: 1) Inform participants of the risk of permanent hearing loss, if an earplug should loosen, become detached, or fall out; 2) Inform participants that they should immediately report to the research staff any loosening or detachment of an earplug during TMS; 3) Immediately stop TMS to replace earplugs if the participants reports or if a staff member observes that an earplug has loosened or has fallen out; 4) Ask the participant if they are experiencing any hearing problems following every session of TMS or if the parent has noticed any hearing problems since the last TMS session; 5) Prompt referral for auditory assessment of all individuals who complain of hearing loss, tinnitus, or aural fullness following completion of TMS.
- **TMS, syncope:** Vasodepressor syncope (fainting) is a common reaction to anxiety and psycho-physical discomfort. It is thought to occur more often than epileptic seizures during TMS, as with many other medical procedures. Participants will be monitored for feeling any signs or symptoms of a pending syncopal event (i.e., feeling dizzy or lightheaded). TMS will immediately be stopped, and the subject will be assisted. See *Management of potential seizures*, above).

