the stimulation groups, and baseline x group interactions. Random effects will be used to model within-subject variation from the first-level analyses. Altogether, the LME will allow us to model how the within-subject change in activation from pre-treatment to post-treatment differs across active and sham conditions. *In addition*, we will also investigate the effects of each TMS regimen on the connectivity in the entire CSTC. To this end, we will extract the ROI-level time courses from each region in the CSTC, and we will use partial correlations to obtain an estimate of connectivity between each ROI pair within the CSTC while accounting for the data observed in the other ROIs. Given the collection of partial correlations for each study participant, we will use the SPU test, which uses the collection of partial correlations simultaneously, to assess for group differences across the sham and TMS regimens.⁷⁵

- Aim 2. Target engagement: Behavior. Hypothesis: Either or both active TMS groups will show within-subject improvement (small effect size of at least Cohen's d = 0.3) in tic suppression ability as measured by the Tic Suppression Task (TST). TST "tic suppression ability" scores will serve as the primary outcome in an ANOVA model. An ANOVA will be used to establish if there exist differences in how the 1Hz, cTBS, and sham conditions affect change in tic suppression ability from pre- to post-treatment. Group indicators for these conditions will be the primary predictors for the model.
- Aim 3. Assess dose-response relationship. Changes in brain (Aim 1) and behavior (Aim 2) targets will be compared between active TMS groups (1Hz rTMS vs. cTBS) using ANOVA. In the case that both active TMS regimens are found superior to sham, we will compare the regimens on safety and feasibility. We will use 2-sample t-tests to compare the two regimens using data from our safety and feasibility measures and prioritize the regimen with significantly better (p<.05) outcomes.
- 15.2. Power Analysis: In Aim 1, hypothesis 1 our proposed sample size after accounting for expected attrition will give us 80% power to detect an effect size of at least $\eta^2=0.18$ for differences in SMA activation between active TMS and sham. For Aim 2, our proposed sample size will give us 80% power to detect an effect size of at least d = 0.90 for a within-subject improvement in tic suppression ability. Our preliminary data showed effect sizes of this magnitude.

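### The only analysis set requires a completed CBIT session, which follows TMS, so a participant who starts TMS and never completes one falls outside the only set available to the Aim 3 safety and feasibility comparison

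*Combined protocol and SAP*

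**What the plan says.** - **Population.** Section 15.1 gives one definition, labelled intent-to-treat: "all enrolled participants who completed at least 1 CBIT session". Neither document part defines a safety, as-treated or any-TMS set.
- **Order of events.** Randomization follows the pre-treatment assessments (5.2, Randomization). Section 4.1 then states: "Immediately prior to each CBIT session, participants will undergo TMS targeting the SMA". The TMS administration text in 5.2 confirms the order: "Immediately after the stimulation ends, the participant will be transitioned to a private room for the CBIT session".
- **Use of safety data.** Section 3.2 lists the comparison of the two active procedures on safety and feasibility as a secondary outcome. Under Aim 3 in 15.1 it is run only when both active regimens have proved superior to sham: "We will use 2-sample t-tests to compare the two regimens using data from our safety and feasibility measures". The regimen that is significantly better at p<.05 is then prioritized. No population is named for these tests, and the measures are not listed.
- **Stopping because of TMS is foreseen.** Section 13.1: "rTMS will be terminated if it produces discomfort which is not tolerated by participants". Section 12.1 lists "significant adverse reaction to TMS" among the reasons for withdrawing a participant.
- **Monitoring.** Section 13.1 has complaints recorded at every visit with TMS. The DSMB in 18.2 reviews adverse events and premature dropout, with no condition on CBIT.

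**The concern.** Entry to the analysis set is decided after randomization and after the first exposure to the assigned stimulation. If that exposure leads a participant to leave for good before completing any CBIT session, the plan's only population leaves that participant out. Membership of a tolerability comparison then depends partly on having tolerated the treatment.

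The two regimens differ at that first exposure: 5.2 gives 33 minutes at 110% of resting motor threshold for 1 Hz, and 40 seconds at 90% for cTBS. Early losses need not be equal. If they are unequal, the regimen with more of them looks better tolerated than it was, in the comparison that is meant to decide which regimen goes forward.

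**Working it through.** No stated figure depends on this definition, so there is none to reproduce. The main check is a reading of the rules against each other; the arithmetic only illustrates size.

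**Who is in and who is out**

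| Course after randomization | In the 15.1 population? |
|---|---|
| Tolerates TMS badly, completes CBIT that day, then quits | Yes |
| Stops TMS on day 1, completes a CBIT session on a later day | Yes (the rule has no time limit) |
| Starts TMS, leaves, never completes any CBIT session | No |

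Only the third row is affected.

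**Inputs**
- Total sample 60 (5.1, 10.1).
- Allocation ratio: not stated. Equal allocation is assumed, so 60/3 = 20 per arm.
- Rate of leaving after first TMS and before any completed CBIT session: not stated. A range of 1% to 5% is assumed. For orientation, 13.1 gives 5% as the overall occurrence of a mild adverse event in sham and real sessions combined, so a 5% rate of permanent early exit would be high.
- Test: two-sample t-test at p<.05 (15.1, Aim 3), taken as two-sided because sidedness is not stated.
- Measure: a 0/1 indicator of early stopping. This too is an assumption.

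**Weight of one loss.** 1/20 = 5 percentage points of an arm.

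**Chance that at least one participant is lost.** 1 − (1 − p)^n:

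| p | one active arm, n = 20 | both active arms, n = 40 |
|---|---|---|
| 1% | 18% | 33% |
| 2% | 33% | 55% |
| 5% | 64% | 87% |

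These are chances of any loss, not of unequal loss. The expected number per arm is 20p: 0.2, 0.4 and 1.0.

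**Effect on the decision rule.** Suppose k of 20 stop early in one regimen and none in the other. The indicator has mean k/20 in the first arm and zero mean and variance in the second. The pooled t statistic then reduces to t = √(19k/(20 − k)) on 38 degrees of freedom.

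| k | t | p, early stoppers included | difference under the 15.1 population |
|---|---|---|---|
| 1 | 1.00 | 0.32 | 0 |
| 2 | 1.45 | 0.15 | 0 |
| 3 | 1.83 | 0.075 | 0 |
| 4 | 2.18 | 0.036 | 0 |
| 5 | 2.52 | 0.016 | 0 |

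At k = 2 a true 10% against 0% is analysed as 0/18 against 0/20, but the rule would not have selected a regimen either way. The rule changes at k = 4. With Fisher's exact test in place of the t-test, k = 4 gives p = 0.106 and k = 5 gives 0.047, so the change would come one participant later.

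**How likely is k = 4?** At p = 5%, the probabilities of 0, 1, 2 and 3 losses in an arm of 20 are 0.358, 0.377, 0.189 and 0.060, which sum to 0.984. Four or more in a given arm therefore has a chance of about 1.6%, before also requiring none in the other arm.

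**The case against.** The strongest reply has four parts.

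1. *Few people can be affected.* Ending a stimulation does not end participation. Section 5.2 lets intensity be adjusted for tolerability, 15.1 keeps participants in the study unless consent is withdrawn or safety is a concern, and 13.1 attaches no known risk to CBIT. This stands, and it is why the expected loss is small. It does not bring the number to zero, because 12.1 provides for withdrawal.
2. *The plan never says that Aim 3 uses this set.* This also stands: the link is an inference from there being only one definition. The definition is labelled intent-to-treat and sits among the missing-data provisions, so its author may have had efficacy in mind. On that reading the safety population is simply unspecified, and the same addition is needed.
3. *The comparison may never be run*, since both regimens must first beat sham. Correct, but when it is run it is the stated basis for choosing between them.
4. *The events are captured anyway.* They are, for recording and for the DSMB. Monitoring does not set the denominator of the regimen comparison.

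A reader might infer more than the text supports: that anyone who stops because of the first TMS session is dropped, that safety data are lost, or that the wrong regimen would probably be chosen. The completion rule has no time limit, the recording and DSMB provisions carry no CBIT condition, and the calculation shows that the p<.05 rule changes on this measure only at a marked imbalance.

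**Conclusion.** The point holds in a limited form. As written, the sole analysis population is conditional on an event after exposure that a bad reaction to TMS can prevent, and the Aim 3 safety and feasibility comparison has no other population to use. The effect is selective on the quantity being compared and can differ by regimen, so an estimate that should reflect early stopping is biased as soon as losses are unequal.

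The likely size is none to a few participants. A changed decision on an early-stop measure alone needs about 4 of 20 against 0, which is unlikely at the rates considered. These figures rest on assumed equal allocation, assumed early-stop rates, a two-sided test, and early stopping being one of the undefined measures. The change is worth making because the bias is avoidable at almost no cost, not because it is likely to be large.

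**What to change.** Add to 15.1:

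- A safety set of all randomized participants who started at least one assigned stimulation session (1 Hz, cTBS or sham), analysed by regimen received, whether or not a CBIT session was completed.
- A statement that the Aim 3 safety and feasibility comparison uses this set, and that stopping because of TMS before completing a first CBIT session counts as a tolerability and feasibility outcome.
- A separate listing of any events in participants who received only motor-threshold pulses. Threshold testing precedes the assigned stimulation, so these participants have received no regimen and cannot be placed in an arm by treatment received.

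The cost is a few sentences. No new data are needed: 13.1 already has side effects and complaints recorded at every TMS visit, and 12.2 has withdrawals documented. Nothing in the conduct of treatment changes.
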